### 8.3.3 CLASSIFICATION OF AN ADVERSE EVENT

#### 8.3.3.1 SEVERITY OF EVENT

- **Mild** – Events require minimal or no treatment and do not interfere with the participant's daily activities.
- **Moderate** – Events result in a low level of inconvenience or concern with the therapeutic measures. Moderate events may cause some interference with functioning.
- **Severe** – Events interrupt a participant's usual daily activity and may require systemic drug therapy or other treatment. Severe events are usually potentially life-threatening or incapacitating. Of note, the term "severe" does not necessarily equate to "serious".

#### 8.3.3.2 RELATIONSHIP TO STUDY INTERVENTION/EXPERIMENTAL MANIPULATION

All AEs will have their relationship to study procedures, including the intervention, assessed by the PI based on temporal relationship and his clinical judgment. The degree of certainty about causality will be graded using the categories below.

- **Definitely Related** – There is clear evidence to suggest a causal relationship, and other possible contributing factors can be ruled out. The clinical event, including an abnormal laboratory test result, occurs in a plausible time relationship to study procedures administration and cannot be explained by concurrent disease or other drugs or chemicals. The response to withdrawal of the study procedures should be clinically plausible. The event must be pharmacologically or phenomenologically definitive.
- **Probably Related** – There is evidence to suggest a causal relationship, and the influence of other factors is unlikely. The clinical event, including an abnormal laboratory test result, occurs within a reasonable time after administration of the study procedures, is unlikely to be attributed to concurrent disease or other drugs or chemicals, and follows a clinically reasonable response on withdrawal.
- **Possibly Related** – There is some evidence to suggest a causal relationship (e.g., the event occurred within a reasonable time after administration of study procedures). However, other factors may have contributed to the event (e.g., the participant's clinical condition, other concomitant events). Although an AE may rate only as "possibly related" soon after discovery, it can be flagged as requiring more information and later be upgraded to "probably related" or "definitely related", as appropriate.

### 8.3.4 TIME PERIOD AND FREQUENCY FOR EVENT ASSESSMENT AND FOLLOW-UP

Recording/reporting of AEs will begin after the subject signs informed consent and end after the subject completes the intervention and follow up period as defined in the protocol.

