### 1.3 SCHEDULE OF ACTIVITIES

	Pre Screen (-60 to 1)	Visit 1 Day 1 a	Visit 2 Day 8 ±14	Visit 3 Day 15 ±7	Visit 4 Day 22 ±7	Visit 5 Day 29 ±7	Visit 6 Day 36 ±7	Visit 7 Day 43 ±14	Visit 8 Day 64 ±14	Visit 9 Day 124±14	For Details, see section
Informed Consent											
Review Study Eligibility b	X										5
Informed Consent c	X										10.1.1
Study Procedures											
Randomization		X									6.3
Demographics		X									8.1
Clinical and Oncologic History		X									8.1
ASI-R		X									8.1
Monitoring											
AS/SAE Assessment			X	X	X	X	X	X	X	X	8.3
Medication Assessment			X	X	X	X	X	X	X	X	8.3
Intervention Administration											
BRIGHT or AC			X	X	X	X	X				6.1
Efficacy Evaluation											
Body Image Scale d	X							X	X	X	8.1
IMAGE-HN d		X						X	X	X	8.1
PROM Assessments											
BICSI d		X						X	X	X	8.1
Shame and Stigma Scale d		X							X	X	8.1
PROMIS SF v1.0- Depression 8a d		X							X	X	8.1
PROMIS SF v1.0- Anxiety 8a d		X							X	X	8.1
PROMIS SF v2.0- Social Isolation 8a d		X							X	X	8.1
PROMIS SF v2.0- Social Roles 8a d		X							X	X	8.1
EORTC QLQ-HN35 d		X							X	X	8.1
Other Evaluations											

Intervention Fidelity		X	X	X	X	X					6.2
Patient Adherence			X	X	X	X					6.4
Program Evaluation								X			8.1
WAI-SR				X			X				8.1

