## 2.3 RISK/BENEFIT ASSESSMENT

### 2.3.1 KNOWN POTENTIAL RISKS

Overall, this research study poses no more than minimal risks to participants. The single-arm pilot study of BRIGHT was a minimal risk study that was approved by the MUSC IRB under an expedited review (45CFR46.110). No formal DSMB was required, although a Data and Safety Monitoring Plan (DSMP) with PI and IRB-based oversight was created. The main study procedures include completion of questionnaires, which are generally considered minimal risk. There are no physical, financial, legal, social, or cultural, risks to the study participants by joining this study. The primary risks of the study are 1) psychological/emotional distress and 2) breach of privacy/confidentiality.

Psychological/emotional distress: Subjects may experience adverse psychological reactions such as anxiety, depression, stress, or distress as a result of discussing issues related to cancer, body image, stigmatization, isolation, coping strategies, or social support. These issues may occur during the completion of study questionnaires (baseline or post-treatment) or during the intervention (BRIGHT or AC). However, based on our prior and ongoing research, we expect that low rates of participant distress and believe that this risk is minimal. Nevertheless, we do have a specific protocol should a participant become distressed as a result of participation in this study. The project coordinator and [name], the study psycho-oncologist both have extensive experience dealing with this patient population and appropriate safeguards have been put in place during our pilot work to mitigate against this risk in either situation.

Breach of privacy/confidentiality: There is also a slight risk that confidential information about the participant may be accidentally disclosed as study participants may be asked to provide information considered confidential or private during study interviews. The likelihood of this risk is low as all the investigators have been involved in similar research in the past and have not experienced this problem before due to adequate safeguards.

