If a participant has a psychological adverse event filling out a questionnaire, the program coordinator will immediately contact [name], a licensed clinical psychologist and the designated study psycho-oncologist, to immediately assess the subject and determine the appropriate course of action. In the event that [name] is not available, a fellow licensed psychologist who works in the HCC Behavioral Medicine program will be contacted. Immediate backup and support will be available. In situations in which suicidal ideation (or other psychiatric emergency) is endorsed during completion of study instruments and [name] or immediate backup is not available, patients will be referred to the emergency room for immediate psychiatric assessment.

Standard safeguards are also in place in case an adverse psychological reaction occurs during a BRIGHT (or AC) telemedicine session. These include determination of the appropriateness of the participant for home-based telemental health care, determination of the adequacy of infrastructure and technology, site assessments and procedures (obtaining patient's address and local 9-1-1/Emergency medical service provider; local provider contact information, alternate patient and emergency contact information), and monitoring of risk during treatment (symptom levels, self-harm ideation, intention to harm others, changes in setting/patient situation) as described in the DSMP.

All cases of possible psychological distress noted by study personnel will be reported to the PI. In situations in which a participant has psychological distress from participation in the study of which the study team is not aware, participants will be encouraged to notify the PI directly. These adverse events will be reported directly to the IRB per protocol. If project staff believe that a subject is distressed by participation in the study, the PI will be notified and will contact the subject to assess distress and assure subject safety.

To help ensure and protect privacy of participants and confidentiality of research data for the study, we will assign a unique study ID number to each subject's information in place of his/her name and will label data collection forms with the ID number. All hard copy and electronic files will be stored appropriately using double-locked methods and password-protection. Only the study team members will have access

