## 8.3 ADVERSE EVENTS AND SERIOUS ADVERSE EVENTS

### 8.3.1 DEFINITION OF ADVERSE EVENTS

This trial is considered to carry a low risk to subjects (i.e. has a "no more than minimal risk" designation). As such, this protocol defines an adverse event (AE) as any undesirable sign, symptom, medical, psychological, social, or emotional reaction that is definitely, probably, or possibly related to the study intervention.

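### AEs and SAEs are defined by the intervention alone, so a reaction caused only by a questionnaire can be escalated under 2.3.3 yet left out of the AE dataset, and baseline reactions are not systematically sought

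*Combined protocol and SAP*

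**What the plan says.** On what counts as an adverse event:

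- Section 2.3.1: "The primary risks of the study are 1) psychological/emotional distress and 2) breach of privacy/confidentiality". It then names two settings in which distress may arise: completing questionnaires, whether at baseline or after treatment, and the BRIGHT or AC sessions.
- Section 2.3.3 sets out what happens "If a participant has a psychological adverse event filling out a questionnaire": the coordinator contacts the study psychologist at once, with a backup path. Distress noticed by staff goes to the PI, and these adverse events go to the IRB.
- Section 8.3.1 limits an AE to a reaction "definitely, probably, or possibly related to the study intervention". Section 8.3.2 limits an SAE to an event directly due to a study intervention.
- Section 8.3.3.2 is wider: "All AEs will have their relationship to study procedures, including the intervention, assessed by the PI".
- Section 8.3.5 collects and reports AEs according to the definition given above it.

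On when events are looked for:

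- Section 8.3.4: "Recording/reporting of AEs will begin after the subject signs informed consent".
- In the Schedule of Activities (1.3), the row printed as "AS/SAE Assessment" (read here as AE/SAE) is marked at Visits 2 to 9. Its Pre Screen and Visit 1 cells are empty. The first marked column is "Visit 2 Day 8 ±14". Most baseline questionnaires are at Visit 1, and consent must come before baseline evaluations.

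**The concern.** The risk section and the definitions do not cover the same ground. A person classifying events from 8.3.1 and a person working from 2.3.3 could reach opposite answers about the same reaction to a questionnaire.

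What is at stake is the completeness of the AE record. Section 8.2 (safety assessments) and section 9.4.4 (safety analyses) are both marked not applicable, and the PI's monthly aggregate review in 10.1.6 works from AEs as recorded. AE records are therefore a main safety output of this pilot. If one of the two named settings of distress enters those records inconsistently, the AE count is hard to interpret and cannot be divided between questionnaires and sessions.

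**Working it through.** No power, sample size or event figure is involved. The check sets the passages side by side and reads one interval from the Schedule.

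**Scope.** Take a participant whose distress is caused only by a questionnaire.

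| Section | Is this reaction covered? |
|---|---|
| 2.3.1 | Yes, as a named primary risk |
| 2.3.3 | Yes, called an adverse event, escalated and reported |
| 8.3.1 | No, because it is not related to the intervention |
| 8.3.2 | No, even if serious, because it is not directly due to an intervention |
| 8.3.3.2 | Relatedness to procedures would be graded, but only for something already classed as an AE |
| 8.3.5 | Collected only if it meets the definition above, which leads back to 8.3.1 |

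Sections 8.3.1 and 8.3.5, followed literally, leave the reaction out of the dataset, while 2.3.3 calls it an adverse event. Section 8.3.3.2 does not settle the matter, because it grades AEs and does not say what qualifies as one. The same holds at Visits 7, 8 and 9, where an AE assessment is marked beside the questionnaires.

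**Timing.** Inputs are the day numbers and windows in section 1.3.

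- Visit 1 to Visit 2, nominal: 8 − 1 = 7 days.
- Visit 1 to the latest Visit 2: 8 + 14 = Day 22, and 22 − 1 = 21 days.
- Earliest Pre Screen day (−60) to Day 22: 81 or 82 days, depending on whether a Day 0 is counted. This is an extreme. Section 10.1.1.2 has consent obtained on the day of enrollment, and 8.1 says screening is generally within 7 days of enrollment.

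**What is given at Visit 1.** Nine instruments are marked. Sections 72-type item counts are not needed for the conclusion, but section 8.1 gives them for eight: ASI-R 20, IMAGE-HN 24, BICSI 29, Shame and Stigma Scale 20, and four PROMIS forms of 8. The sum is 20 + 24 + 29 + 20 + (4 × 8) = 125 items, before the EORTC QLQ-HN35. This describes exposure to questionnaires. It is not an estimate of missed events, and the documents give no rate from which to make one.

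**The case against.** A reader might infer that reactions to questionnaires escape safety capture altogether. The documents do not support that.

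- Section 2.3.3 is an operative rule, with immediate escalation and reporting to the PI and the IRB.
- An empty Schedule cell does not bar recording. Section 8.3.4 opens the period at consent, so an event seen or volunteered at Visit 1 falls inside it, and nothing limits the Visit 2 assessment to events after the first session.
- Someone who withdraws before Visit 2 has the reason recorded on the CRF (7.2), and early withdrawals are reviewed monthly (10.1.6).
- Section 2.3.1 expects little distress, and 2.3.3 reports past use of these measures without undue distress.
- The minimal-risk designation is made in advance and is not derived from this trial's AE counts.

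All of this stands, and it sets the size of the point. It does not remove the inconsistency. Section 2.3.3 depends on staff noticing distress or the participant volunteering it, and the Schedule footnotes allow questionnaires by mail or email, where staff may see nothing. Its reporting to the IRB is per protocol, which leads back to section 8.3. The unanticipated-problem route in 8.4.1 refers to participation in the research, but it also requires the event to be unexpected. Distress listed as a known risk would usually not qualify.

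**Conclusion.** The point holds as an internal inconsistency of minor severity. A reaction caused only by a questionnaire would be managed under 2.3.3, yet could be left out of the formal AE dataset because 8.3.1, 8.3.2 and 8.3.5 are narrower than 2.3.1, 2.3.3 and 8.3.3.2. Separately, baseline reactions are not systematically sought: the first scheduled assessment comes 7 days after Visit 1 nominally, and up to 21 days at the window limit.

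It would go too far to say that such events are under-counted by a known amount or that participants are unprotected. No efficacy result changes.

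The conclusion rests on two readings: that the Schedule row means AE/SAE assessment, and that the column order of the table as extracted is right, so that its eight marks are Visits 2 to 9.

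**What to change.** 1. In 8.3.1 and 8.3.2, word relatedness as study procedures, including questionnaires and the intervention, so that both agree with 2.3.3 and 8.3.3.2. Changing 8.3.1 alone would leave a serious questionnaire reaction outside the SAE definition.
2. In 1.3, add an AE/SAE mark at Visit 1, after the baseline questionnaires, covering events since consent. The look-back makes a separate Pre Screen mark unnecessary.
3. Add a field to the AE form for the source: questionnaire or session.

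The cost is protocol wording, one Schedule mark and one eCRF field. The downside is a few more mild AEs recorded. Section 9.2 refers to interim accrual data, so enrollment had begun: the Visit 1 mark helps only participants still to come, while the aligned definition can also be applied to reactions already noted. Design, sample size and treatment are unaffected.

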### 8.3.5 ADVERSE EVENT REPORTING

All AEs, as defined above, will be collected and reported. Data collection will occur via electronic spreadsheet. The information will be saved in REDCap and managed by the study team. In consultation with the PI, a trained member of the study team will be responsible for conducting an evaluation of a SAE and shall report the results of such evaluation to the NIH and the reviewing Institutional Review Board (IRB) as soon as possible and in accordance with the reviewing IRB policy

---

#### 8.3.6 SERIOUS ADVERSE EVENT REPORTING

In consultation with the PI, a trained member of the study team will be responsible for conducting an evaluation of a SAE and shall report the results of such evaluation to the NIH and the reviewing IRB as soon as possible and in accordance with the reviewing IRB policy.

---

#### 8.3.7 REPORTING EVENTS TO PARTICIPANTS

N/A

---

#### 8.3.8 EVENTS OF SPECIAL INTEREST

N/A

---

#### 8.3.9 REPORTING OF PREGNANCY

N/A

### 8.4 UNANTICIPATED PROBLEMS

---

#### 8.4.1 DEFINITION OF UNANTICIPATED PROBLEMS

This protocol uses the definition of Unanticipated Problems (Ups) as defined by the Office for Human Research Protections (OHRP). OHRP considers unanticipated problems involving risks to participants or others to include, in general, any incident, experience, or outcome that meets all of the following criteria:

- Unexpected in terms of nature, severity, or frequency given (a) the research procedures that are described in the protocol-related documents, such as the IRB-approved research protocol and informed consent document; and (b) the characteristics of the participant population being studied;
- Related or possibly related to participation in the research (“possibly related” means there is a reasonable possibility that the incident, experience, or outcome may have been caused by the procedures involved in the research); and
- Suggests that the research places participants or others at a greater risk of harm (including physical, psychological, economic, or social harm) than was previously known or recognized.

---

#### 8.4.2 UNANTICIPATED PROBLEMS REPORTING

The investigator will report UPS to the reviewing IRB and to the lead PI. The UP report will include the following information:

- Protocol identifying information: protocol title and number, PI's name, and the IRB project number
- A detailed description of the event, incident, experience, or outcome
- An explanation of the basis for determining that the event, incident, experience, or outcome represents an UP
- A description of any changes to the protocol or other corrective actions that have been taken or are proposed in response to the UP

To satisfy the requirement for prompt reporting, UPs will be reported using the following timeline:

- Ups will be reported to the IRB and to the NCI in accordance with policy regarding timeliness of reporting
- All UPs should be reported to appropriate institutional officials (as required by an institution's written reporting procedures), the supporting agency head (or designee), and the OHRP in accordance with policy regarding timeliness

#### 8.4.3 REPORTING UNANTICIPATED PROBLEMS TO PARTICIPANTS

N/A

## 9 STATISTICAL CONSIDERATIONS

### 9.1 STATISTICAL HYPOTHESES

- Primary Endpoint:

We hypothesize that, compared with patients who receive the AC, patients who receive BRIGHT will have reduced BID as measured by change in BIS scores at 1-month post-intervention relative to baseline. Alternatively, our null hypothesis is that there will be no difference between BRIGHT and AC in terms of improving BID, as measured by change in BIS scores at 1-month post-intervention relative to baseline.

[figure not shown]
- Secondary Endpoint(s):

We hypothesize that improvements in body image coping behavior (improvement in BICSI scores from baseline to 1-week post intervention) will partially mediate a decrease in BID (reduction in BIS scores from baseline to 1-month post intervention) and this relationship will be maintained at 3-months.

We hypothesize that BRIGHT will improve psychological (larger decrease in Shame and Stigma scores), emotional (larger decrease in PROMIS depression and anxiety scores), and social well-being (larger decrease in PROMIS social roles and social isolation scores) relative to AC at 1- and 3-months post-intervention.

### 9.2 SAMPLE SIZE DETERMINATION

Our primary objective is to compare change in BIS scores from baseline to 1-month intervention between the BRIGHT and AC arms. The primary endpoint is  $\Delta$  in Body Image Scale scores from baseline to 1-month post-intervention. We hypothesize that, compared with patients who receive the AC, patients who receive BRIGHT will have reduced BID as measured by change in BIS scores at 1-month post-intervention relative to baseline. Alternatively, our null hypothesis is that there will be no difference between BRIGHT and AC in terms of improving BID, as measured by change in BIS scores at 1-month post-intervention relative to baseline. All power and sample size calculations were performed using PASS 2008 version 08.0.13. Based on data from our prospective cohort study and single-arm pilot of BRIGHT, we estimate the mean  $\Delta$  in Body Image Scale scores  $\pm$  SD from baseline to 1-month post are  $0.2 \pm 5.9$  and  $4.6 \pm 3.9$  for control and BRIGHT, respectively. This effect size is clinically significant and realistic given results of other psychobehavioral interventions in breast cancer patients with BID. For n=22/arm (proposed sample size), power exceeds 80% for mean difference in change in Body Image Scale scores of at least 3.1 (with SD as large as 4) or mean difference of at least 5.5 (with SD as large as 7) based on two-sided t-test with  $\alpha=0.1$  (**Fig. 4A**). Group sample size of n=22 (AC, BRIGHT) achieved 80.2% power to detect the standardized effect (mean difference in  $\Delta$  Body Image Scale score from baseline to 1-month divided by the pooled SD=5.62) of 0.78 based on the two-sample t-test with two-sided  $\alpha=0.1$  (**Fig 4B**). We will have greater than 90% power for a standardized effect size of 0.93 and greater than 80% power for a standardized effect size of 0.78. These are both considered moderate effect sizes and are feasible for continuous outcomes in the context of variables that are expected to be modulated by the cancer experience. Our power estimate is conservative given our proposed analysis plan using LME regression, which borrows strength over time and is generally more efficient than a t-test. As such we anticipate that smaller effect sizes than described above will be detectable. Our selection of relaxed significance ( $\alpha = 0.1$ ) with maintained power ( $1 - \beta = 0.8$ ) is based on the desire to emphasize power over type I error at this

**Fig. 4. Power Calculations for (A)** Mean difference in  $\Delta$  in Body Image Scale scores between baseline and 1-month post intervention, comparing BRIGHT and AC; **(B)** standardized effect, comparing  $\Delta$  in Body Image Scale scores between BRIGHT and AC from baseline to 1-month post intervention

early stage of development (single-site pilot RCT) to ensure follow-up on promising interventions to guide and power a subsequent larger RCT to fully evaluate the efficacy of BRIGHT as a treatment of BID in HNC survivors (i.e. test BRIGHT with significance level of 0.05). We therefore consider our RCT to be appropriately and rigorously designed to detect a clinically meaningful reduction in BID.

In order to have 44 patients eligible for the efficacy analysis in the modified ITT population (see **Section 9.3, Population for Analyses**), we plan to enroll 52 patients. Our sample size is inflated by 20% based on interim accrual data. This inflation account for study dropout and the predictable subset of patients would be enrolled in the study, be randomized to BRIGHT or AC, receive a portion or all of the intervention and then subsequently are withdrawn from the study and non-evaluable due to a major HNC surgery or recurrent or second primary cancer.

Every effort will be made to minimize missing data and lost-to-follow-up participants. Participants will complete assessments at baseline, 1-week post-intervention, 1-month post-intervention, and 3-months post intervention using an iPad-based REDCap collection method. The program coordinator will attempt to contact patients at least three times using a variety of methods of communication (e.g. text message, phone call, email, mail, etc.) to complete outcome measures. This method resulted in 100% instrument completion in our single arm pilot study. In the event that missing data do occur, we will address them via standard multiple imputation procedures. As participants will be randomized to treatment, it is unlikely that missing data will produce biased estimates of treatment effect, as observed and unobserved covariates should theoretically be balanced across treatment groups. In general, less than 10% missing data has little impact on study power and does not induce bias regardless of the missing data mechanism^55. If missing data is greater than 10%, it will be imputed using propensity score or Markov Chain Monte Carlo (MCMC) methods. When covariate information is associated with whether the imputed variable values are missing, we will use the propensity score method, which calculates the propensity score from modeling the distribution of the missing indicator variable based on the observed data and then applies an approximate Bayesian bootstrap imputation to each group identified by the propensity score. Otherwise, we will use the MCMC method. The data augmentation will be applied to Bayesian inference with missing data by repeating imputation step (i.e., simulating the missing values based on the observation) and step for exploring the posterior distribution based on the complete sample estimates obtained from the imputation step.

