## 9.4 STATISTICAL ANALYSES

### 9.4.1 GENERAL APPROACH

Graphical displays such as scatterplots and boxplots will be constructed to demonstrate patterns of individual continuous measures and differences between baseline, 1-week, 1- and 3-months post intervention. Summary descriptive statistics (e.g. frequencies and percent for categorical variables, and mean, median, standard deviation, and range for continuous variables) will be reported. For inferential tests, we will use a p-value of 0.05, two-sided, and 95% confidence intervals (CIs) to assess statistical significance (Type I error). Covariates will be pre-specified as described below. Normality of the data will be assessed before underlying statistical procedures will be performed. We will evaluate variable transformations as needed to satisfy assumptions and consider transformations of variables to induce approximate normality and stabilize variance as needed. Nonparametric tests will be applied when appropriate.

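### Section 9.2 powers the trial at two-sided alpha 0.10, but section 9.4.1 tests at two-sided 0.05, where the same design has about 71.5% power, not 80.2%; the planning SD of 5.62 is unexplained.

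*Combined protocol and SAP*

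**What the plan says.** Section 9.2 takes its planning values from two earlier studies: "Based on data from our prospective cohort study 50 and single-arm pilot of BRIGHT". The mean changes in Body Image Scale score, with SDs, "from baseline to 1-month post are $0.2 \pm 5.9$ and $4.6 \pm 3.9$ for control and BRIGHT, respectively". The power statement is "Group sample size of n=22 (AC, BRIGHT) achieved 80.2% power to detect the standardized effect" of 0.78, which is defined as the mean difference in change "from baseline to 1-month divided by the pooled SD=5.62) of 0.78 based on the two-sample t-test", at two-sided alpha 0.10. The section adds a claim of "greater than 90% power for a standardized effect size of 0.93 and greater than 80% power for a standardized effect size of 0.78". It defends the relaxed alpha as a choice to favour power over type I error in an early single-site pilot, and links the 0.05 level to a later, larger trial.

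Section 9.4.1 sets a different rule for this trial: "we will use a p-value of 0.05, two-sided, and 95% confidence intervals (CIs) to assess statistical significance". Section 9.4.2, which describes the primary mixed-model analysis, names no significance level. Section 9.2 does not say how 5.62 was obtained, and neither section gives the size of the cohort behind the control SD.

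**The concern.** The two sections give different error rates for the same trial. If 9.4.1 governs, the power in 9.2 was computed for a test that will not be used. If 9.2 governs, the intervals announced in 9.4.1 do not match the test. The primary conclusion then depends on which section is applied, and that choice could be made after the p-value is known.

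The SD adds to the problem. With 1:1 allocation one expects the two stated SDs to pool with equal weight, and they do not give 5.62. The choice of SD decides whether the planned difference of 4.4 points reaches 80% power at 0.05, so power cannot be restated for one agreed alpha until the basis of the SD is stated.

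**Working it through.** **Inputs**
- Mean change 0.2 (control) and 4.6 (BRIGHT), so the difference is 4.4; SDs 5.9 and 3.9; 22 per arm; pooled SD 5.62; two-sided alpha 0.10 (all section 9.2).
- 1:1 allocation (section 6.3).
- Pilot: 9 patients with a 1-month result, mean decrease 4.56, 95% CI 1.55 to 7.56 (section 2.2.7).
- Two-sided alpha 0.05 (section 9.4.1).

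**Method.** Two-sample t-test power from the noncentral t with df = 42 and noncentrality d × √(22/2) = 3.317d. The two-sided critical values are 1.682 at 0.10 and 2.018 at 0.05.

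**1. The plan's own figure.** 4.4/5.62 = 0.783, which the plan rounds to 0.78. At d = 0.78 the noncentrality is 2.587 and power at 0.10 is 81.6% (81.8% at d = 0.783). The stated 80.2% is 1.4 points lower, a small gap on the cautious side. The other statements in 9.2 also hold at 0.10:
- d = 0.93: 91.8%
- 3.1 points with SD 4: 81.2%
- 5.5 points with SD 7: 82.1%

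**2. The same design under the rule in 9.4.1.** At alpha 0.05, d = 0.78 gives 71.5% and d = 0.783 gives 71.8%.

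**3. Consequence for the decision.** With SD 5.62, the standard error of the difference is 5.62 × √(2/22) = 1.694. The smallest significant observed difference is 1.682 × 1.694 = 2.85 points at 0.10 and 2.018 × 1.694 = 3.42 points at 0.05. An observed difference between these two values would be judged differently by the two sections.

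**4. The SD for two equal arms.** √((5.9² + 3.9²)/2) = √((34.81 + 15.21)/2) = 5.00, and d = 4.4/5.00 = 0.88. Power is 89.0% at 0.10 and 81.4% at 0.05. A Welch test, which allows unequal variances, gives 88.8% and 81.1%.

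**5. Where 5.62 could come from.** The pilot interval returns the BRIGHT SD: half-width (7.56 − 1.55)/2 = 3.005; divided by t(0.975, 8 df) = 2.306 and multiplied by √9, this is 3.91. So n = 9 is the natural weight for 3.9. The cohort size is not in the documents and is an assumption here. Weighting variances by degrees of freedom:
- cohort n = 41: √((40 × 34.81 + 8 × 15.21)/48) = 5.616
- cohort n = 42: √((41 × 34.81 + 8 × 15.21)/49) = 5.622

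Both round to 5.62. If the pilot n were 10 or 11, the cohort n would have to be 46–47 or 51–52.

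| SD | d for 4.4 points | Power at 0.10 | Power at 0.05 |
|---|---|---|---|
| 5.62 (as stated) | 0.78 | 82% | 72% |
| 5.00 (equal arms) | 0.88 | 89% | 81% |

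**The case against.** The strongest defence has three parts.

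First, 9.2 is the specific section and 9.4.1 the general one. The authors chose 0.10 openly and linked 0.05 to a later trial, so 0.10 could be taken to govern the primary test. That is a reasonable guess at intent, but the text does not say it. Section 9.4.1 covers inferential tests without exception, and 9.4.2 names no alpha that would override it.

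Second, 9.2 calls its t-test power conservative because the mixed model uses repeated measures. That may be so, but the plan does not quantify the gain, so it cannot be credited with closing a gap of some 8 points.

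Third, a reader might infer that 5.62 is an arithmetic error and that effect size and power are therefore misstated. The documents do not support this. 4.4/5.62 does give 0.78, and 80.2% is close to the exact value for that effect. Weighting by source-study size is a standard way to pool two historical samples. The 1:1 allocation fixes the weights in the future test, not the way in which a planner estimates an assumed common SD. Equal weighting would also let an SD from nine patients count for half. Any departure lowers d and power, and both 5.00 and 5.62 lie within the SD range of 4 to 7 that 9.2 considers. This part of the defence stands. What remains is that 9.2 does not say how the figure was derived.

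Nor do the documents support the inference that 5.62 conceals that 0.10 was unnecessary. Section 9.2 does not argue that 80% power is out of reach at 0.05, and whether it is depends on the SD: 72% with 5.62, 81% with 5.00.

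**Conclusion.** The conflict over alpha is an error in the plan as written. For the stated effect of 0.78 at 22 per arm, power is about 81.6% at two-sided 0.10 and about 71.5% at two-sided 0.05. The 80.2% in 9.2 therefore does not apply under the rule in 9.4.1. Any primary p-value between 0.05 and 0.10 would be read in opposite ways.

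The SD is a lesser point. 5.62 is not the equal-arm pooled value (5.00), but it is compatible with weighting by source-study size and it errs on the cautious side. It is unexplained, not proven wrong, and the trial is not underpowered at 0.10 on its own assumptions.

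These results assume the plan's means and SDs, 44 evaluable patients split equally, and a two-sample t-test as in 9.2. The account of 5.62 also rests on a cohort size that the documents do not give.

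**What to change.** 1. Name one two-sided alpha for the primary test, with the matching interval level (90% for 0.10, 95% for 0.05), and use it in both 9.2 and 9.4.1. If other tests keep 0.05, say so in 9.4.1.
2. Restate power in 9.2 for that alpha. With SD 5.62 and a difference of 4.4 points it is about 82% at 0.10 or 72% at 0.05. Giving both lets the reader see the cost of the choice.
3. State how 5.62 was obtained, including the sizes of the two source samples, or label it a cautious planning SD. Add the equal-arm figures as a sensitivity: SD 5.00, standardised effect 0.88, power 89% at 0.10 and 81% at 0.05.

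The cost is rewording in two sections. The sample size does not change. The choice of alpha should be fixed before the outcome data are examined.
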